## 8. STUDY OBJECTIVES AND ENDPOINTS

## 8.1 Study Objectives

The objectives of the study are to assess safety, tolerability, preliminary efficacy and PK of multiple SC doses of APL-2 in subjects with a primary diagnosis of wAIHA who relapsed from, did not respond to, or did not tolerate at least one prior wAIHA treatment regimen (such as prednisone, rituximab, or splenectomy), or a primary diagnosis of CAD regardless of prior treatment history.

An exploratory objective of the study is to assess the PD of multiple SC doses of APL-2 when administered to AIHA patients.

## 8.2 Study Endpoints

## **Primary Safety Endpoints:**

The primary safety endpoints of the study are the incidence and severity of treatment emergent adverse events (TEAEs) following administration of multiple doses of SC APL-2.

## Efficacy Endpoints:

- Change from baseline in Hb
- Number of red blood cell (RBC) transfusions during study
- Change from baseline in absolute reticulocyte count
- Change from baseline in LDH
- Change from baseline in haptoglobin
- Change from baseline in indirect bilirubin
- APL-2 serum concentrations (and pharmacokinetic (PK) parameters as appropriate
- Change from baseline in Functional Assessment of Chronic Illness Therapy (FACIT) scale and the Linear Analog Scale Assessment scale (LASA) including energy level, ability to perform daily activity, and overall quality of life (QoL)

## Exploratory PD markers include:

- Complement (e.g., CH50, AP50, and C3) activity and levels
- C3 deposition on RBC cells

## STUDY DESIGN

This is a Phase II, open-label, prospective pilot study of APL-2 conducted in subjects with a primary diagnosis of wAIHA or CAD in parallel. The study will consist of up to 24 subjects, up to 12 subjects with a primary diagnosis of wAIHA in Cohort 1 and up to 12 subjects with a primary diagnosis of CAD in Cohort 2. Subjects in each cohort will be randomly (1:1) assigned to receive either 270 mg/d or 360 mg/d of APL-2 treatment for up to 12 months (Part A, the Core Study Phase).

Following Day 336 and the completion of the Part A Core Study Phase, subjects will be eligible to participate in Part B, a Long-term Extension Phase, in order to continue to receive treatment with APL-2. The Long-Term Extension Phase is described in Section 17.3.1.

Through Part A (Day 336), dose escalation from 270 mg/d to 360 mg/d, or de-escalation from 360 mg/d to 270 mg/d may occur after thorough evaluation of available safety and laboratory assessment.

Safety will be assessed throughout the study; serial blood and urine samples will be collected for these assessments. Blood samples will be collected for the assessment of APL-2 PK. Additional samples for assessment of PD will also be collected.

Screening will take place within 30 days prior to the start of dosing on Day 1. If needed (see inclusion criteria), *Neisseria meningitides* types A, C, W, Y and B (administered as two separate vaccines), PCV13 or PPSV23, and Hib vaccinations will be administered prior to dosing on Day 1.

Subjects who meet all the inclusion criteria and none of the exclusion criteria will be enrolled into the study on Day 1 at a time designated by the PI. During study, the first 3 daily SC doses of APL-2 (Day 1 to 3) as well as doses on Day 7 and 14 will be administered at the clinical site. From Day 4 to Day 336 daily doses of APL-2 will be administered off-site by a study nurse or self-administered by the subject and/or caregiver, at the subject's home, workplace, or other location convenient to the subject with the exception of those days where dosing is at the clinical site. At any time during the study, if subjects discontinue treatment, or if after the conclusion of the Part A Core Study Phase a subject does not elect to enter the Part B Long-Term Extension Phase, subjects will return to the clinical site for safety follow-up study procedures after 6 weeks, followed by final study procedures at an Exit Visit after another 6 weeks. See Study Flowchart in Section 3.

The planned length of participation in the study for each subject is at least approximately 450 days (from Day –30 through completion of the Day 420 Exit visit procedures [for subjects that do not elect to enter the Part B Long-Term Extension Phase]). Subjects that continue in the Part B Long-Term Extension Phase may continue to receive indefinitely until the subject discontinues or the development program is terminated. The study duration may change in the event that the study is terminated early, additional subjects are needed, additional time is required to review safety between groups, or extended safety and PK sampling is added for a dose group (e.g. beyond Day 420).

## 10. SUBJECT SELECTION

The study is planned to enroll up to 24 subjects, with up to 12 subjects in Cohort 1 with a primary diagnosis of wAIHA and up to 12 subjects in Cohort 2 with a primary diagnosis of CAD.

Subjects should not be rescreened once they have been designated as a screen failure, unless this is discussed in advance and documented in writing with the sponsor.

## 10.1 Inclusion Criteria

At Screening (unless otherwise specified), subjects must fulfill all of the following inclusion criteria to be eligible for participation in the study:

- 1. At least 18 years of age.
- 2. Weight <125 Kg.
- Subjects must have a primary diagnosis of wAIHA or CAD defined by the presence of hemolytic anemia and positive DAT for wAIHA (IgG) or CAD (C3).
- 4. Hemoglobin <11 g/dL.
- 5. Signs of hemolysis with abnormal values by any of the hemolytic markers:
  - a. Increased absolute reticulocyte count (above ULN)
  - b. Reduced haptoglobin (below LLN)
  - c. Increased lactase dehydrogenase (LDH) (above ULN)
  - d. Increased indirect bilirubin (above ULN)
- 6. Women of child-bearing potential (WOCBP) (defined as any female who has experienced menarche and who is NOT permanently sterile or postmenopausal. Postmenopausal is defined as 12 consecutive months with no menses without an alternative medical cause) must have a negative pregnancy test at screening and must agree to use protocol defined methods of contraception for the duration of the study and 90 days after their last dose of study drug.
- Males must agree to use protocol defined methods of contraception and agree to refrain from donating sperm for the duration of the study and 90 days after their last dose of study drug.
- 8. Able to provide documentary evidence of the following vaccinations within 2 years prior to screening:
  - a. Neisseria meningitides types A, C, W, Y and type B (administered as two separate vaccinations)
  - Streptococcus pneumoniae (Pneumococcal conjugate vaccine and Pneumococcal polysaccharide vaccine 23 [PCV13 and/or PPSV23, respectively])
  - c. Haemophilus influenzae Type B (Hib) vaccine

Subjects that do not have documentary evidence must be willing to receive any missing vaccinations as outlined below:

- a. Neisseria meningitides types A, C, W, Y and type B must be administered prior to dosing on Day 1. A booster is administered after at least 8 weeks (Day 56; for both vaccinations).
- Streptococcus pneumoniae PCV13 must be administered prior to dosing on Day 1 (see Section 12.2 for details). A PPSV23 booster is administered after at least 8 weeks (Day 56)
- c. Haemophilus influenze Type B (Hib) must be administered prior to dosing on Day

  1.
- 9. Willing and able to give informed consent.
- 10. Specific for wAIHA: Relapsed from, did not respond or relapsed, or did not tolerate, at least one prior wAIHA treatment regimen (such as prednisone, rituximab).

## 10.1.1 Approved Methods of Contraception

Approved methods of contraception include: oral contraceptives, intrauterine device, medically acceptable barrier methods (diaphragm or condom), implantable or injectable contraceptives (like Depo-Provera) or removable birth control device (like NuvaRing® or Ortho Evra patches); and/or surgical sterilization (at least 6 months before dosing). Subjects practicing abstinence and coitus interruptus (pull out method) must agree to use an additional approved method of contraception during the study and 90 days after their last dose of study drug.

## 10.2 Exclusion Criteria

Subjects will be excluded from the study if there is evidence of any of the following criteria at screening or check-in, as appropriate.

- 1. Prior treatment with rituximab within 90 days.
- 2. Deficiency of iron, folic acid and vitamin B12 prior to treatment phase.
- Abnormal liver function as indicated by elevated AST or ALT. Any elevation of AST or ALT level >2x upper limit of normal (ULN) will require Sponsor review and approval for subject enrollment into the trial.
- 4. Elevated bilirubin not due to active hemolysis. Any elevation of bilirubin >ULN will require Sponsor review and approval for subject enrollment into the trial.
- 5. Active aggressive lymphoma requiring therapy or an active non-lymphatic malignant disease other than basal cell carcinoma or CIS of the cervix.
- Presence or suspicion of active bacterial or viral infection, in the opinion of the Investigator, at screening or severe recurrent bacterial infections.
- 7. Participation in any other investigational drug trial or exposure to other investigational agent, device, or procedure within 30 days prior to screening period.

- Pregnant, breast-feeding, or intending to conceive during the course of the study, including the Post-Treatment Phase.
- Inability to cooperate or any condition that, in the opinion of the investigator, could
  increase the subject's risk by participating in the study or confound the outcome of the
  study.
- 10. Myocardial infarction, CABG, coronary or cerebral artery stenting and /or angioplasty, stroke, cardiac surgery, or hospitalization for congestive heart failure within 3 months or > Class 2 Angina Pectoris or NYHA Heart Failure Class >2
- 11. QTcF > 470 ms
- 12. PR > 280 ms
- 13. Mobitz II 2nd degree AV Block, 2:1 AV Block, High Grade AV Block, or Complete Heart Block unless the patient has an implanted pacemaker or implantable cardiac defibrillator (ICD) with backup pacing capabilities

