## 4.1.3 Rational for Treatment with APL-2

Complement plays an important role in warm antibody AIHA. On erythrocytes heavily coated with immunoglobulin, the amount of antigen-antibody complex can be sufficient for binding complement protein complex C1 and, thereby, for activation of the classical complement pathway. Moreover, complement activation plays a significant role in CAD, which is entirely a complement-dependent disorder (Berentsen, 2015). Cold antibodies (IgM) temporarily bind to the RBC membrane, activate complement, and deposit complement factor C3 on the cell surface. These C3-coated RBCs are cleared slowly by the macrophages of the liver through extravascular hemolysis. Less frequently, the complete complement cascade is activated on the cell surface, resulting in the insertion of membrane attack complex C5b to C9 and intravascular hemolysis (Dhaliwal, 2004).

Current available treatments for patients with AIHA are far from satisfactory. Available treatments include steroids, RBC transfusions, immunosuppressants, splenectomy, and Rituximab off label use. Long-term use of corticosteroids is known to be associated with many complications, RBC transfusions may exacerbate hemolysis with the potential risk to develop hyperhemolysis and RBC alloantibodies resulting in an inadequate recovery due to autoantibodies will react with donor cells in AIHA patients (Wouters, 2015). RBC transfusions should be restrictive and specific precautions need to be undertaken to avoid severe transfusion reactions and alloimmunization with increased transfusion problems (Berentsen, 2015). On the other hand, the sustained response rate for wAIHA after splenectomy is approximately 60-70% according to the most recent data with a peri-operative risk and a mortality rate of less than 1% (Reynaud, 2015). However, overwhelming sepsis and postoperative cytotoxic immunosuppressants can also be associated with serious adverse events. Treatment with Rituximab monotherapy has been shown in prospective studies to induce remission in approximately half of the patients with CAD, although complete remissions are unusual and the medical response duration is only 1 year (Berentsen, 2015). Given the toxicity of rituximab and concern of adverse effects, a balanced assessment of benefit and risk should be considered in treating AIHA patients (Berentsen, 2012).

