reduction of downstream C5 that mediates intravascular hemolysis. Encouraging signs of activity were also observed with APL-2 monotherapy in 3 treatment-naïve PNH patients in the New Zealand phase 1b study APL-2-CP-PNH-204; however, variability in observed responses in this small population suggests additional dose-ranging higher than 270 mg, may be warranted.

- The proposed APL2-CP-AIHA-208 monotherapy trial in AIHA patients targets only C3.
  Given the incomplete understanding of APL-2 monotherapy dose-response in PNH
  patients as described above, the inclusion of two doses of APL-2, 270 mg/day and 360
  mg/day, in the proposed AIHA study will support identification an optimal dose for this
  new disease indication as a C3 complement inhibition monotherapy.
- The proposed 360 mg/day dose is estimated to reach approximately 73% of the Cmax of the NOAEL observed in monkeys after 273 days SC dosing. In addition, Apellis has completed two clinical studies investigating the safety, tolerability, and PK of single APL-CP-0713-1 subcutaneous doses (including 360 mg, and a maximum dose of 1440 mg), and single APL2-CP-HV-401 intravenous doses (up to 2300 mg) of APL-2 in healthy volunteers. Maximum doses from both of these studies appeared to be safe and well tolerated and are estimated to reach approximately 23% and 65% respectively of the Cmax of the NOAEL observed in monkeys. Further support of safety and tolerability comes from emerging data from 2 patients receiving APL-2 360 mg/day for up to 2 months in the ongoing PNH Phase 1b trials.

The self-administration pump can be programmed to deliver in volumes of one mL increments, and no fractions of thereof. As a result, when delivering a dose of 270 mg, a nominal dose of up to 280 mg may be delivered dependent upon the concentration of the formulation (e.g. formulation 40 mg/mL administered in 7mL provides a dose of 280 mg). This difference of approximately 4% is considered an acceptable margin which will have minimal/no impact on the PK/PD or efficacy of APL-2.

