## Per Protocol (PP) Set:

The PP Set will include subjects who complete Part A Core Study Phase (Visit 15) and who have not violated any inclusion or exclusion criteria and/or deviated from the protocol in a way that could influence their efficacy assessment through Visit 15. Decisions concerning the exclusion of subjects from this set will be made and documented during an adjudication by DPC and the sponsor prior to database lock. Baseline characteristics, demographics and efficacy endpoint data will be presented using the PP Set.

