## 5.3.4 Efficacy Laboratory Parameters

Efficacy laboratory parameters include the following:

- 1. Hemoglobin
- 2. Lactate Dehydrogenase
- 3. Reticulocytes
- 4. Haptoglobin
- 5. Indirect Bilirubin

Individual data will be listed by along with changes from baseline and percent changes from baseline.

Results, changes from baseline, and percentage changes from baseline will be summarized, using descriptive statistics, at each scheduled study visit by randomized dose group and cohort, in addition to overall.

All individual results will be plotted by actual study day, where each subject will be identifiable. The mean results  $\pm$  SE for each scheduled visit by dose group and cohort will also be plotted. Individual and mean changes from baseline  $\pm$  SE will also be plotted similarly.

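### Efficacy values recorded after a steroid, rituximab or other immunosuppressant is started or raised on study count as change on APL-2, in both the ITT and PP sets

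*Protocol*

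**What the plan says.** **Rules on other therapy.** Protocol 10.2 excludes "Prior treatment with rituximab within 90 days", and that section's criteria apply "at screening or check-in, as appropriate", so this is an entry rule. Protocol 11.4 (Concomitant Medications) covers prophylactic and rescue antibiotics, iron and folic acid. Iron doses must be held stable. There is no rule for corticosteroids, rituximab or other immunosuppressants during treatment. Protocol 12.1 collects dose and duration of earlier treatment, naming steroids and rituximab.

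**Analysis sets.** The Part A SAP (4.2) keeps in the PP Set subjects who complete Visit 15 and have not violated an entry criterion or "deviated from the protocol in a way that could influence their efficacy assessment through Visit 15". The Part B SAP (4.1) builds its PP Set from the Part A one, with the same kind of rule. Part A SAP 5.1.2 defines a deviation as a departure from the design or procedures set out in the protocol.

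**Efficacy summaries.** Part A SAP 5.3.4 states: "Results, changes from baseline, and percentage changes from baseline will be summarized, using descriptive statistics, at each scheduled study visit by randomized dose group and" (the second grouping factor is the disease cohort). Section 5.3.1 divides all transfusions in a study part by all days in that part. Part B SAP 5.3.1 and 5.3.4 follow the same pattern by cohort, for ITT and PP.

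**Medications.** Both SAPs list concomitant medications and count subjects by drug class and name. Neither links them to an efficacy value.

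**The concern.** The trial has no untreated control, so change from baseline is the main evidence of preliminary efficacy, and Protocol 7.1 says the results will guide further development. If hemolysis continues on APL-2 and a steroid is raised or rituximab begun, any later recovery enters the mean as change on APL-2. The subjects doing worst are the most likely to be given more therapy, so the error can favour the drug.

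A reader would expect the PP tables to be protected from this, and they are not. Completing Visit 15 is itself a condition of the Part A PP Set, so a subject who stays on study with the help of added therapy still qualifies.

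**Working it through.** The plan states no effect size, power or sample-size calculation, so there is no figure of its own to reproduce. The check follows one case through the documents and then sizes it.

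**Step 1: follow a subject whose prednisone is raised, or rituximab started, after Day 1.**
- Protocol 10.2: the rituximab criterion has already been passed at entry.
- Protocol 11.4: no rule has been broken.
- SAP deviation definition: with no rule broken, there is no deviation.
- PP definitions, Parts A and B: no entry violation and no deviation, so the subject stays in. The adjudication before lock has no stated criterion on which to act.
- Sections 5.3.1 and 5.3.4 of both SAPs: all later values and days enter the ITT and PP summaries.
- Subgroup sections (Part A 4.6, Part B 4.5): no subgroup analysis is planned.

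The affected values are therefore not separated at any stage.

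**Step 2: size.** Inputs:
- n = 6 per dose group and 12 per cohort, the planned maxima (Protocol synopsis).
- d = Hb rise not due to APL-2. The documents give no figure; 1 to 3 g/dL is assumed.
- k = number of affected subjects.

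Shift in the group mean = k × d / n.

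| Group | k | d = 1 g/dL | d = 3 g/dL |
|---|---|---|---|
| Dose group, n = 6 | 1 | 1/6 = 0.17 | 3/6 = 0.50 |
| Dose group, n = 6 | 2 | 2/6 = 0.33 | 6/6 = 1.00 |
| Cohort, n = 12 | 1 | 1/12 = 0.08 | 3/12 = 0.25 |

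Because 6 and 12 are maxima, a smaller group at a late visit would give a larger shift for the same k and d. The Part B SAP tabulates by cohort, so the cohort row applies there.

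**Step 3: compare with the PK plan.** Part A SAP 5.4 summarises concentrations twice: for everyone as randomized, and only for subjects on their randomized dose at the visit. It also drops samples taken more than 1 day after the last dose. The SAP thus already shows an all-values summary beside a restricted one for PK. The efficacy sections have no counterpart.

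**The case against.** **What can fairly be said for the plan.** This is a pilot with a safety primary endpoint, exploratory efficacy and no inferential statistics. Medications are listed, and Part A efficacy values are plotted by actual day with each subject identifiable, so in groups of six or fewer a reader can look for affected subjects. An investigator may refuse entry for a condition that could confound the outcome. An all-values summary is also legitimate in itself. These points lower the stakes, but inspection afterwards is not a planned rule, and the entry discretion does not reach therapy added later. Protocol Section 17.3 and the SAP appendices were not in the text examined, so Part B medication rules and the output lists could not be checked.

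**Stronger readings that the documents do not support.**
- *A reader might infer that rituximab carry-over is credited to APL-2, because 90 days is shorter than the response the protocol cites.* Protocol 4.1.3 does say "complete remissions are unusual and the medical response duration is only 1 year". But entry requires Hb below 11 g/dL and at least one abnormal hemolytic marker, and baseline is the last pre-dose value on Day 1. A response already present is in the baseline, and if it wanes the change from baseline falls, which counts against APL-2. Only a response that begins or deepens after Day 1 would favour APL-2, and the documents give no time to onset. The transfusion baseline covers the prior 365 days and may include time under rituximab, so that bias can also go either way. How much of Part A a one-year response would overlap measures time, not spurious Hb gain.
- *A reader might apply the one-year figure to both cohorts.* It is given for rituximab monotherapy in CAD, said to "induce remission in approximately half of the patients with CAD". No figure is given for wAIHA.
- *A reader might take "The proposed APL2-CP-AIHA-208 monotherapy trial in AIHA patients targets only C3" to mean that background AIHA therapy is absent.* In Protocol 7.2.1 the contrast is with APL-2 added to eculizumab, so the word refers to complement inhibition alone. It does not contradict Section 11.4.

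**Conclusion.** The point holds for therapy started or raised on study. Neither the protocol text examined nor either SAP says how efficacy values after such use are handled, and the PP sets do not fill the gap. One affected subject would shift a full dose-group mean Hb change by 0.17 to 0.50 g/dL and a full cohort mean by 0.08 to 0.25 g/dL.

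Those figures illustrate scale and do not estimate the bias. They rest on an assumed rise of 1 to 3 g/dL, and the documents permit such use without showing that it occurs or how often. The direction rests on a further assumption, that therapy is added mainly when APL-2 is not working.

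Earlier rituximab is a secondary matter. Its direction is unknown, and it warrants marking the subjects concerned but no claim of upward bias.

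**What to change.** Keep every planned all-values table. In Sections 5.3.1 and 5.3.4 of both SAPs, add the following.

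1. **Flag.** Before database lock, a medical review of the coded concomitant medications identifies each subject's first on-study start or dose increase of an AIHA-directed therapy (corticosteroid, rituximab or other immunosuppressant).
2. **Laboratory markers.** For each efficacy marker, add one supportive by-visit summary in which values after the flag are replaced by the subject's last value before it. Show the number flagged at each visit. Do not simply drop the later values: if poor responders are the ones flagged, dropping them leaves mainly responders at late visits and can raise the mean. Carrying the value forward keeps them in the denominator.
3. **Transfusions.** Add a rate for transfusions and units that uses only days before the flag.
4. **Marking.** Show the flag date, and any rituximab within 365 days before Day 1, in listings and individual plots.

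For change from Part B baseline, the SAP should also say how a subject already flagged in Part A is treated, because that baseline then follows the added therapy.

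**Cost.** One medication review, one extra table per endpoint, and possibly a less favourable Hb change. The carried value is a simplification: it may be a low point reached just before therapy was added. A transfusion rate over few days is unstable. Both summaries should therefore be labelled supportive. All subjects stay in, so this is not a subgroup analysis, and no change to eligibility or care is proposed.
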